### 3.7 Statistical Analysis Outline

In the RCT (**Part 2**), all analyses will be performed on participants randomised to **Part 2** only, on an intention-to-treat basis with sensitivity analyses run on the per protocol population.

The primary outcome measure is change in nodule hardness from baseline to 12 months. There will only be one dose level used in **Part 2**, which will be 40mg of adalimumab. It is expected that all nodules will be large enough to accommodate the injection, but if not the volume of residual IMP will be recorded. The difference in the mean change of nodule hardness between the two groups will be reported with 95% confidence intervals. The comparison of change in nodule hardness between interventions will be analysed primarily using Analysis of Covariance (ANCOVA) adjusting for baseline, if it is normally distributed. As a secondary confirmatory analysis, ANCOVA adjusting for baseline nodule hardness as well as the stratification factors comprising centre (Oxford, Edinburgh or Groningen) and age (as a continuous variable) will be conducted.

If the data are not normally distributed, the data will be log-transformed in order to gain normality and geometric means with 95% confidence intervals will be reported. If data are not normally distributed after log-transformation, the non-parametric Mann Whitney test will be used with no adjustment for baseline, and the median change with 95% confidence intervals will be reported.

In order to analyse change in nodule hardness over the full time period, linear mixed effects regression will be used to compare nodule hardness between interventions utilising all time-points up to 18 months and adjusting for stratification and other important prognostic factors.

The secondary outcome measures for **Part 2** include those for **Part 1** and also grip strength, range of motion and participant reported outcomes.

For nodule size, grip strength, range of motion of the affected digit, Michigan Hand Outcomes Questionnaire, patient identified activity most restricted by DD, progression to surgery, and injection experience linear mixed effects regression models will be used. This procedure will allow for data from all follow-up time-points to be accounted for, and for adjustment for baseline measures to be made, where applicable. The time (days) between baseline injection and each follow-up time-point will be included in the models as a random effect to account for patients not all having their follow-up assessments at the same time.

Repurposing anti-TNF for treating Dupuytren's disease (funded by Health Innovation Challenge Fund, Wellcome Trust)  
EudraCT Number: 2015-001780-40 and OCTRU Reference Number CTU0028

As per the primary outcome, initial analyses for all secondary outcomes will be unadjusted and additional adjusted analyses will be carried out further accounting for centre (Oxford, Edinburgh or Groningen) and age (as a continuous variable) and baseline if appropriate. For all models, assessments for interaction between time since baseline treatment and baseline measurement will be carried out to assess if any effect of baseline measurement changes over time.

For all secondary outcome analyses, mean difference and associated 95% confidence intervals will be reported. If severe departures from normality are identified in secondary outcome measurements, the data will be log-transformed in order to gain normality and geometric means with 95% confidence intervals will be reported. If the data are not normally distributed – or near normally distributed – after log transformation, the non-parametric Mann-Whitney test will be used with no adjustment for baseline, and the median change with 95% confidence intervals will be reported.

## 4. STATISTICAL PRINCIPLES

### 4.1 Statistical Significance and Multiple Testing

There is no multiple testing as only a single primary objective is considered. Therefore, significance levels used will be 5%, and 95% confidence intervals will be reported. Secondary outcomes will also be analysed using a significance level of 5% and 95% confidence intervals as these are considered supportive of the primary conclusion only. Other outcomes will be considered exploratory and hypothesis generating only.

No interim analysis of primary and secondary endpoints are planned but, if requested by the DSMC, a 0.1% significance ( $\alpha=0.001$ ) will be used.

### 4.2 Definition of Analysis Populations

Intention-to-treat (ITT): All participants analysed in their randomised groups with available outcome data.

Per-protocol (PP): The ITT population with some participants excluded. Patients will be excluded from per-protocol analysis if they did not satisfy the study eligibility criteria or did not receive the allocated treatment. The definition of the per-protocol population will be finalised during a blinded analysis of data (not separated by treatment arm) prior to the final data-lock.

Safety: All participants who started their allocated treatment, that is, those received at least one of the intervention injections they were allocated to, as defined in the protocol.

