### **11.1. Inclusion in Analysis**

The intention-to-treat population is all randomised participants, grouped by the treatment allocated as opposed to the treatment received.

The per-protocol population includes those participants who complied with the protocol in terms of eligibility, treatment and availability of outcome measurements. Full details of the exclusions from this population will be detailed in the SAP.

The safety population is made up of all participants who started treatment, that is, who received at least one injection.

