### Treatment compliance

A summary of the treatment received, i.e. the number of injections, will be presented. If patients did not receive their intended allocation at any time-point, this will be defined as non-compliant and will be reported.

Participant compliance and treatment compliance will be examined by observing the difference in non-adherence between the two treatment arms.

Non-adherence to the protocol and reasons, such as withdrawals, will be summarised. In addition, the number of patients for which the visit does not take place within the specified window will be summarised for the two treatment arms.

**Appendix 5: Treatment compliance, Table 6:** Treatment compliance: Number of adalimumab and saline injections received according to intervention allocated.

**Appendix 5: Treatment compliance, Table 7:** Treatment deviations: Treatment received according to intervention allocated.

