### Safety analysis

Adverse events are recorded as a secondary outcome in the RIDD RCT.

A Serious Adverse Event (SAE) is any untoward medical occurrence that results in death, is life-threatening, requires inpatient hospitalisation or prolongation of existing hospitalisation, results in persistent or significant disability/incapacity, or consists of a congenital anomaly or birth defect. All potentially related SAEs must be recorded on the trial specific SAE form and reported within 24 hours to the Study Site Team becoming aware of the event. Causality must be assessed by a medically qualified doctor. The SAE form must be sent to the Trials office. The SAE form will also be sent to an independent clinician as soon as all relevant information is available but no later than 3 calendar days from when the trial office is made aware of the event as per OCTRU SOPs for safety reporting. The independent clinician will assess the SAE for causality and expectedness and provide a response as per OCTRU safety reporting. In the event where the independent clinician disagrees with the assessment of the site PI, a discussion will be encouraged between the two to reassess the event. If either the PI or the independent clinician continue to assess the event as related, both assessments will be recorded. If the event is also serious and unexpected this will be reported as a SUSAR by the Trials Office to the MHRA, Ethics and Sponsor as per below. All related SAEs will be followed until resolved or not further information is expected. SAEs will only be considered closed when signed off by the local PI.

The safety analysis will be carried out on the safety population (see **Section 4.2**). Details for any related SAEs and SUSARs will be reported. Should sufficient numbers be reported comparison of patients experiencing related SAEs and SUSARs between the two treatment groups will be undertaken by examining 95% confidence intervals for the difference in incidence. An overall category for any SAE will also be compared.

The injection site will be monitored for adverse events using an 'Injection Site Response' Form, which is collected shortly after receiving each treatment. Frequency and percentages for types of AEs reported will be presented. Where sufficient numbers of AEs are reported, chi-squared tests will be used for comparing intervention groups at each follow-up time-point. *P*-values will be reported to 3 decimal places.

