## 18. TREATMENT COMPLIANCE

**Table 8:** Treatment compliance: Number of adalimumab and saline injections received according to treatment allocated

Injections Received	Saline		Adalimumab		Total	
	N =	%	N =	%	N =	%
	n	%	n	%	n	%
Adalimumab						
1						
2						
3						

Repurposing anti-TNF for treating Dupuytren's disease (funded by Health Innovation Challenge Fund, Wellcome Trust)  
EudraCT Number: 2015-001780-40 and OCTRU Reference Number CTU0028

	Saline		Adalimumab		Total	
	N =	%	N =	%	N =	%
Injections Received	n	%	n	%	n	%
4						
Saline						
1						
2						
3						
4						

**Table 9:** Treatment deviations: Treatment received according to treatment allocated. Percentages calculated as of each time-point

	Saline		Adalimumab		Total	
	N =	%	N =	%	N =	%
Injection Received	n	%	n	%	n	%
Baseline						
Adalimumab						
Saline						
3 months						
Adalimumab						
Saline						
6 months						
Adalimumab						
Saline						
9 months						
Adalimumab						
Saline						

Repurposing anti-TNF for treating Dupuytren's disease (funded by Health Innovation Challenge Fund, Wellcome Trust)  
EudraCT Number: 2015-001780-40 and OCTRU Reference Number CTU0028

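### The SAP's safety population leaves out anyone injected only with the product they were not allocated to; the protocol includes them

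*SAP*

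**What the plan says.** Protocol 11.1 defines the set by exposure alone: "The safety population is made up of all participants who started treatment, that is, who received at least one injection". In the same section, the distinction between allocation and receipt appears only for the intention-to-treat population, which is "grouped by the treatment allocated as opposed to the treatment received".

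SAP 4.2 brings allocation into the safety definition twice. It begins with "All participants who started their allocated treatment" and then explains this as "those received at least one of the intervention injections they were allocated to, as defined in the protocol". The definition is operative, because the Safety analysis text in SAP 6.4 states: "The safety analysis will be carried out on the safety population", with a cross-reference to Section 4.2.

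The SAP also provides for injections that do not match the allocation. SAP 5.5, under Treatment compliance, says: "If patients did not receive their intended allocation at any time-point, this will be defined as non-compliant and will be reported". Dummy Table 9 in section 18 of the table appendix is titled "Treatment deviations: Treatment received according to treatment allocated" and has adalimumab and saline rows under both allocated arms at each of the four injection visits.

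**The concern.** A safety population should contain everyone exposed to a trial injection. Making entry depend on receiving the allocated product removes people because of a dispensing or administration error, and those people were still exposed. The example that matters most is a saline-allocated participant who received only adalimumab. Such a person was exposed to the drug, yet would be missing from both numerator and denominator of the comparison of harms.

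The exclusion need not be unrelated to harm. It does not take four wrong injections: one wrong first injection followed by stopping treatment is enough. Protocol 8.8 lists both adverse events and significant protocol deviations among the reasons for stopping.

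Part 2 already records few events. Protocol 10.3 limits recorded adverse events to grade 3 or above that are attributed to the medication or its injection, and Protocol 10.4 limits reported SAEs to related ones, in both cases up to 28 days after the last injection. When few events are expected, one omitted participant can matter.

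**Working it through.** The plan gives no figure to reproduce, so the check compares the two rules for each pattern of exposure.

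Inputs: the two definitions (Protocol 11.1, SAP 4.2); four planned injections (Protocol section 6, Part 2); a minimum of 69 per arm (Protocol 11.3, SAP 3.3); a maximum of 200 participants randomised 1:1 (Protocol section 6, Part 2).

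Let k be the number of injections received (0 to 4) and m the number of those that were the allocated product. The protocol rule is k ≥ 1. The SAP rule is m ≥ 1.

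| Pattern | k | m | Protocol 11.1 | SAP 4.2 |
|---|---|---|---|---|
| No injection | 0 | 0 | out | out |
| All as allocated | ≥ 1 | = k | in | in |
| Mixed products | ≥ 2 | 1 to k − 1 | in | in |
| None as allocated | ≥ 1 | 0 | **in** | **out** |

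The rules differ only in the last row.

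Next, does anything else in the documents put these participants back? Nothing does. The change log in SAP 1.2 lists no change to the safety population, and no other SAP section gives a different safety set.

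Then, could the word allocated mean no more than scheduled? The entry just before it in SAP 4.2 excludes from the per-protocol set those who did not receive the allocated treatment, and SAP 5.5 treats departure from the intended allocation as non-compliance. In this SAP the word refers to the randomised product. The SAP can also define a set by receipt when it means to: SAP 6.4 examines circulating drug levels in participants who had at least one adalimumab injection.

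Weight of one participant:

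- At the minimum size: 1 / 69 = 1.4% of an arm.
- At the maximum size: 200 / 2 = 100 per arm, and 1 / 100 = 1.0% of an arm.

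These figures show what one affected participant would weigh. They do not estimate how many there are, which the documents do not give.

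**The case against.** The strongest reply is that this is loose paraphrase. The SAP sentence appeals to the protocol and the change log records no decision to narrow the set, so the intention was probably to follow Protocol 11.1. That is likely true, but an analyst who applies SAP 4.2 as written gets the narrower set.

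A second reply is that the affected pattern is rare. A participant must never have received the allocated product. Table 9 is an empty shell and SAP 5.5 a general reporting rule, so neither shows that such a participant is expected. This stands: the group may be empty.

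Third, a reader might infer that harms in these participants vanish altogether. The documents do not support that. Related SAEs after the first injection go to the Trial Office whether or not the product matched (Protocol 10.4), SUSARs are reported with the code broken (Protocol 10.6), the injection site form is collected after each treatment (SAP 6.4), and wrong-product injections are tabulated. What is lost is the participant's place in the comparison between arms.

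Fourth, a reader might infer that a saline-allocated participant given both products stays in the saline group, so that adalimumab harms count against placebo. That is possible, but it is not a stated rule. SAP 4.2 specifies analysis in randomised groups for the intention-to-treat set only. For safety it defines who is in, and SAP 6.4 compares the groups without saying whether they are as allocated or as received. Mixed-exposure participants have no stated arm.

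**Conclusion.** The SAP definition is wrong as written. It adds a condition that Protocol 11.1 does not contain, attributes it to the protocol, and so excludes from the comparative safety analysis anyone injected only with the non-allocated product. This conclusion rests on the wording of the two sections and on no assumption about rates.

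The practical effect depends on a count that the documents do not give. It is probably very small and may be zero, with each affected participant worth about 1.0% to 1.4% of an arm. The intention-to-treat efficacy analysis is not touched. The point still merits correction because the sentence determines who is counted for harms. The absence of a grouping rule is a separate gap, not part of the contradiction.

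**What to change.** In SAP 4.2, replace the safety definition with the protocol's: all participants who received at least one injection of either product, whatever their allocation. This follows directly from Protocol 11.1.

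As a suggestion for the separate gap, add a sentence to SAP 4.2 or to the Safety analysis text in SAP 6.4 saying that safety is summarised by treatment received, with a rule for mixed exposure. One reasonable convention is to count anyone with at least one adalimumab injection as exposed to adalimumab. Neither document prescribes this, so it is a choice for the trial team and should be made before the data are unblinded.

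The cost is a few lines of SAP text. No new data or protocol amendment is needed, since the SAP already plans to tabulate the product received at each injection visit.

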## 5. TRIAL POPULATION AND DESCRIPTIVE ANALYSES

Descriptive analysis will include a summary flow of participants through the trial and baseline stratification, demographic, and clinical characteristics of each treatment group.

### 5.1 Representativeness of Study Sample and Patient Throughput

The flow of participants through each stage of the trial, including numbers of participants assessed, randomly assigned to adalimumab or saline injection, receiving their assigned treatment, completing the study protocol, and analysed for the primary outcome will be provided in a flow diagram as suggested by CONSORT. Protocol violations/deviations and information relating to the screening data including the number of ineligible patients

Repurposing anti-TNF for treating Dupuytren's disease (funded by Health Innovation Challenge Fund, Wellcome Trust)

EudraCT Number: 2015-001780-40 and OCTRU Reference Number CTU0028

randomised, participants found to be ineligible and participants who refused to participate will also be provided, with reasons where available.

**Appendix 5: Trial Recruitment, Figure 1:** CONSORT flow diagram of participants in the trial.

## 5.2 Withdrawal from treatment and/or follow-up

The numbers (with percentages) of losses to follow-up (defaulters and withdrawals) will be reported and compared between the adalimumab and saline groups. To ensure that there are not differential losses between the groups this will be tested using absolute risk differences and associated 95% confidence intervals, and a Chi-squared test. Any deaths (and their causes) will be reported separately.

**Appendix 5: Trial recruitment, Table 1:** Patient withdrawals and reasons according to intervention groups.

**Appendix 5: Trial recruitment, Table 2:** Number of participants with data available at each time-point by intervention allocated.

## 5.3 Baseline Comparability of Randomised Groups

The patients in the two treatment arms will be described both overall and separately in terms of stratification factors (centre and age).

Numbers (with percentages) for binary and categorical variables and means (and standard deviations), or medians (with lower and upper quartiles) for continuous variables will be presented; there will be no tests of statistical significance nor confidence intervals for differences between randomised groups on any baseline variable.

**Appendix 5: Baseline comparability of randomised groups, Table 3:** Categorical demographic baseline characteristics according to intervention allocated.

**Appendix 5: Baseline comparability of randomised groups, Table 4:** Continuous demographic baseline characteristics according to intervention allocated.

**Appendix 5: Baseline Comparability of randomised groups, Table 5:** Clinical characteristics according to intervention allocated.

## 5.4 Unblinding

Participants and healthcare professionals involved in participant follow-up and outcome assessment will always be blinded to treatment allocation. Laboratory staff will be blinded to treatment allocation. Due to the distinctive appearance of the pre-filled syringes, it is not possible to blind the healthcare professional administering the injection.

All cases of treatment unblinding will be listed, together with who was unblinded, reasons for unblinding and summarised (numbers and percentages).

## 5.5 Description of Compliance with Intervention

Compliance with the intervention will be summarised for both treatment arms, with compliance being reported as both participant compliance and treatment compliance.

Repurposing anti-TNF for treating Dupuytren's disease (funded by Health Innovation Challenge Fund, Wellcome Trust)  
EudraCT Number: 2015-001780-40 and OCTRU Reference Number CTU0028

### Participant compliance

Participants will be defined as being compliant if they have received at least 75% of injections, that is, receiving three out of the four injections offered.

### Treatment compliance

A summary of the treatment received, i.e. the number of injections, will be presented. If patients did not receive their intended allocation at any time-point, this will be defined as non-compliant and will be reported.

Participant compliance and treatment compliance will be examined by observing the difference in non-adherence between the two treatment arms.

Non-adherence to the protocol and reasons, such as withdrawals, will be summarised. In addition, the number of patients for which the visit does not take place within the specified window will be summarised for the two treatment arms.

**Appendix 5: Treatment compliance, Table 6:** Treatment compliance: Number of adalimumab and saline injections received according to intervention allocated.

**Appendix 5: Treatment compliance, Table 7:** Treatment deviations: Treatment received according to intervention allocated.

## 5.6 Reliability

Validation checks will be performed in order to check calculations and processes performed by a computer program by hand-checking a random sample of the largest of 5% of the available data or 20 patients. This will include if data have been imported and merged correctly. Prior to analysis, further validation checks will ensure that data are of the appropriate format, for example, within the maximum possible range of values. For example, when summary scores are calculated, these will be checked by hand calculations. Clarification will be sought by the trial office in the case of discrepancies.

## 6. ANALYSIS

### 6.1 Outcome Definitions

#### Primary outcome

Nodule hardness from baseline to 12 months: The primary outcome is hardness of nodule selected for treatment measured at 12 months post-first injection using a validated portable durometer. During the initial stages of this study researchers within the team noted that the original portable durometer being used to measure nodule hardness in the UK-based centres was potentially unable to achieve accurate measurements in patients with moderate to severe deformities of their hands due to their DD. Following this an alternative durometer with a longer probe, which would be able to overcome this issue, was sourced. To ensure patients who had nodule hardness data collected using only the original durometer were not excluded from analyses, or included with inaccurate data, all subsequent patients recruited in the UK-based centres had their nodule hardness data collected with both the original and the new portable durometer. The centre in the Netherlands only recorded data using the newer portable durometer.

The outcomes for RIDD were tested in our ultrasound study (REC Ref. 11/SC/0047) 'Ultrasonographic (grey scale) characteristics of DD and their relationship to the clinical features and functional severity of the disease: a pilot study'. Preliminary (unpublished) tonometry data from 25 patients in this trial demonstrated that the

Repurposing anti-TNF for treating Dupuytren's disease (funded by Health Innovation Challenge Fund, Wellcome Trust)

EudraCT Number: 2015-001780-40 and OCTRU Reference Number CTU0028

palmar tissue of patients with untreated DD were significantly firmer than the corresponding age and sex matched controls.

Using the measurements from the portable durometers, the amount of indentation is converted to hardness reading on a scale with 100 units (internationally standardised durometer units). The time window for collecting the primary end-point nodule hardness data will allow  $\pm$  4 weeks to confer some flexibility. This will be extended to  $\pm$  3 months where physical measurements could not be safely recorded due to the SARS-CoV-2 pandemic.

